17.7. LABORATORY EVALUATIONS

Central laboratory results will be included in the reporting of this study for Hematology, Clinical Chemistry, Coagulation, and Urinalysis. Viral serology, urine drug and alcohol screening, pregnancy and FSH levels will be assessed as part of subject screening to determine eligibility. A list of laboratory assessments to be included in the outputs is included in Appendix 3 of the protocol, Table 6. Presentations will be in SI Units, as provided by the labs.

Protocol-specified clinical laboratory tests will be summarized using descriptive statistics. Clinical laboratory data collected during study conduct, which were not required per protocol, such as for special testing to further evaluate an AE, will be listed separately and not summarized.

Quantitative laboratory measurements reported as “< X”, i.e. below the lower limit of quantification (BLQ), or “> X”, i.e. above the upper limit of quantification (ULQ), will be converted to X for the purpose of quantitative summaries, but will be presented as recorded, i.e. as “< X” or “> X” in the listings.

The following summaries will be provided for laboratory data:

- Observed and change from baseline to Day 14 (for quantitative measurements).

Document: Statistical Analysis Plan
Author: [REDACTED]

Version Number: 2.0
Version Date: 03APR2019

[REDACTED]

- Incidence of abnormal values according to normal range criteria
- Shift from baseline according to normal range criteria (for quantitative measurements and categorical measurements) for Day 14.

17.7.1. LABORATORY REFERENCE RANGES AND MARKEDLY ABNORMAL CRITERIA

Quantitative laboratory measurements will be compared with the relevant laboratory reference ranges by the lab vendors and categorized as:

- Low: Below the lower limit of the laboratory reference range.
- Normal: Within the laboratory reference range (upper and lower limit included).
- High: Above the upper limit of the laboratory reference range.

Clinical laboratory reference/normal ranges will be provided separately and results outside the normal range criteria will be flagged as such in the listings.

17.8. ECG EVALUATIONS

Results of the ECG assessments will be included in the reporting of this study. For Cohort A the results of 12-lead ECG results will be listed; whereas for triplicate ECG measurements taken for Cohort B the average over the triplicate readings will also be presented in addition to the individual triplicate assessment results.

The following ECG parameters will be reported for this study (ms): PR, QRS, QT, QTc, QTcF, QTcB, and HR (bpm). The average of triplicate readings in Cohort B will be used for all analysis purposes.

Overall assessment of ECG (Investigator's judgment) will be recorded as following:

- o Normal
- o Abnormal, Not Clinically Significant (ANCS)
- o Abnormal, Clinically Significant (ACS)

The following summaries will be provided for ECG data:

- Actual and change from baseline (for quantitative measurements and all post-baseline assessments) by study day as well as for the screening visit.
- Shift from baseline according to overall assessment of ECG, as judged by the Investigator, by study day for all post-baseline assessments.

17.8.1. CLINICALLY NOTEWORTHY ECG CRITERIA

Clinically noteworthy quantitative ECG measurements will be identified in accordance with the following criteria:

- Observed values for QTcF will be classified as:
 - > 450 msec
 - > 480 msec
 - > 500 msec
- Change from QTcF will be classified as:
 - >30 msec increase from baseline
 - >60 msec increase from baseline

17.9. VITAL SIGNS

The following Vital Signs measurements will be reported for this study:

- Sitting Systolic and Diastolic Blood Pressure (mmHg)
- Pulse Rate (bpm)
- Respiratory Rate (breaths/min)
- Temperature (°C)

The following summaries will be provided by treatment for vital signs data:

- Observed and change from baseline for all post-baseline assessments.

17.10. PHYSICAL EXAMINATION

Physical exam results will be listed including the date and time of assessment, specification of any abnormalities, and any changes noted from baseline to post-baseline assessment.

18. DATA NOT SUMMARIZED OR PRESENTED

The details of the telephone call on Day 30 (Study Exit) will not be mapped to the SDTM/ADaM databases except for subject reported adverse events or concomitant medications. These details will be available in the clinical database.

Document: Statistical Analysis Plan
Author: [REDACTED]

Version Number:
Version Date:

2.0
03APR2019

APPENDIX 1. PROGRAMMING CONVENTIONS FOR OUTPUTS

This appendix (including the example layout) is optional, depending on the customer. Include if no customer guidelines, otherwise reference customer guidelines

OUTPUT CONVENTIONS

Outputs will be presented according to the [REDACTED] Global Biostatistics Standard Output Conventions, which is available upon request.

DATES & TIMES

Depending on data available, dates and times will take the format yyyy-mm-dd; times will take the format hh:mm:ss; combined dates and times will take the format yyyy-mm-ddThh:mm:ss.

SPELLING FORMAT

English US

PRESENTATION OF TREATMENT GROUPS

For most safety outputs, data will be summarized by treatment groups and will be represented as follows and in that order:

Treatment Group	For Tables
OP0201 30 mg	OP0201 30 mg administered intranasally (2 sprays per nostril) TID for 14 consecutive days
OP0201 60 mg	OP0201 60 mg administered intranasally (4 sprays per nostril) TID for 14 consecutive days
All Active	All Active Treated Subjects
All Placebo	All Placebo Treated Subjects
All Subjects	All Treated Subjects

Some safety outputs will summarize data by cohorts and treatment groups, they will be represented as follows and in that order:

Treatment Group	For Tables
Cohort A, Overall	OP0201 30 mg or Placebo administered intranasally (2 sprays per nostril) TID for 14 consecutive days
Cohort A, OP0201 30 mg	OP0201 30 mg administered intranasally (2 sprays per nostril) TID for 14 consecutive days

Document: Statistical Analysis Plan

Author: [REDACTED]

Version Number:

2.0

Version Date:

03APR2019

Treatment Group	For Tables
Cohort A, Placebo	Placebo administered intranasally (2 sprays per nostril) TID for 14 consecutive days
Cohort B, Overall	OP0201 60 mg or Placebo administered intranasally (4 sprays per nostril) TID for 14 consecutive days
Cohort B, OP0201 60 mg	OP0201 60 mg administered intranasally (4 sprays per nostril) TID for 14 consecutive days
Cohort B, Placebo	Placebo administered intranasally (4 sprays per nostril) TID for 14 consecutive days
All Active	All Active Treated Subjects
All Placebo	All Placebo Treated Subjects
All Subjects	All Treated Subjects

PRESENTATION OF VISITS

For safety outputs, except those related to AEs, visits will be represented as follows and in that order:

Treatment Period	Visit Name(s)
Screening Day -28 to -1	Screening
Confinement Period	Day -1, Day 1, Day 4, Day 8, Day 14, Day 15
Study Exit	ET, Day 21 Follow-up

ET=Early Termination

PRESENTATION OF NOMINAL TIMES

For PK outputs, nominal times will be represented as follows and in that order:

Analyte	Cohort	Nominal Timepoints
DPPC	B	Day 1: 60 mins Predose, and 30 mins Predose; Day 14: 30 mins Predose, 5 mins, 20 mins, 35 mins, 50 mins

LISTINGS

All listings will be ordered by the following (unless otherwise indicated in the template):

- Cohort
- Unique Subject ID

- Study Day
- Assessment date and time

Document: Statistical Analysis Plan
Author: [REDACTED]

Version Number:
Version Date:

2.0
03APR2019

APPENDIX 2. PARTIAL AND MISSING DATE CONVENTIONS

Imputed dates will NOT be presented in the listings.

ALGORITHM FOR TREATMENT EMERGENCE OF ADVERSE EVENTS:

START DATE	STOP DATE	ACTION
Known	Known	If start date < study med start date, then not TEAE If start date >= study med start date, then TEAE
	Partial	If start date < study med start date, then not TEAE If start date >= study med start date, then TEAE
	Missing	If start date < study med start date, then not TEAE If start date >= study med start date, then TEAE
Partial, but known components show that it cannot be on or after study med start date	Known	Not TEAE
	Partial	Not TEAE
	Missing	Not TEAE
Partial, could be on or after study med start date	Known	If stop date < study med start date, then not TEAE If stop date >= study med start date, then TEAE
	Partial	Impute stop date as latest possible date (i.e. last day of month if day unknown or 31st December if day and month are unknown), then: If stop date < study med start date, then not TEAE If stop date >= study med start date, then TEAE
	Missing	Assumed TEAE
Missing	Known	If stop date < study med start date, then not TEAE If stop date >= study med start date, then TEAE
	Partial	Impute stop date as latest possible date (i.e. last day of month if day unknown or 31st December if day and month are unknown), then: If stop date < study med start date, then not TEAE If stop date >= study med start date, then TEAE
	Missing	Assumed TEAE

ALGORITHM FOR PRIOR / CONCOMITANT MEDICATIONS:

START DATE	STOP DATE	ACTION
Known	Known	If stop date < study med start date, assign as prior If stop date >= study med start date and start date <= end of treatment, assign as concomitant If stop date >= study med start date and start date > end of treatment, assign as post study
	Partial	Impute stop date as latest possible date (i.e. last day of month if day unknown or 31 st December if day and month are unknown), then: If stop date < study med start date, assign as prior If stop date >= study med start date and start date <= end of treatment, assign as concomitant If stop date >= study med start date and start date > end of treatment, assign as post treatment
	Missing	If stop date is missing could never be assumed a prior medication If start date <= end of treatment, assign as concomitant If start date > end of treatment, assign as post treatment
Partial	Known	Impute start date as earliest possible date (i.e. first day of month if day unknown or 1 st January if day and month are unknown), then: If stop date < study med start date, assign as prior If stop date >= study med start date and start date <= end of treatment, assign as concomitant If stop date >= study med start date and start date > end of treatment, assign as post treatment
	Partial	Impute start date as earliest possible date (i.e. first day of month if day unknown or 1 st January if day and month are unknown) and impute stop date as latest possible date (i.e. last day of month if day unknown or 31 st December if day and month are unknown), then: If stop date < study med start date, assign as prior If stop date >= study med start date and start date <= end of treatment, assign as concomitant If stop date >= study med start date and start date > end of treatment, assign as post treatment

START DATE	STOP DATE	ACTION
	Missing	Impute start date as earliest possible date (i.e. first day of month if day unknown or 1 st January if day and month are unknown), then: If stop date is missing could never be assumed a prior medication If start date <= end of treatment, assign as concomitant If start date > end of treatment, assign as post treatment
Missing	Known	If stop date < study med start date, assign as prior If stop date >= study med start date, assign as concomitant Cannot be assigned as 'post treatment'
	Partial	Impute stop date as latest possible date (i.e. last day of month if day unknown or 31 st December if day and month are unknown), then: If stop date < study med start date, assign as prior If stop date >= study med start date, assign as concomitant Cannot be assigned as 'post treatment'
	Missing	Assign as concomitant

MISSING DATES FOR CERTAIN ECG / PK ASSESSMENTS:

The dates on certain triplicate ECG assessments and pre-dose PK sample collections were not recorded in source data as per the CRF design resulting in missing date values in the corresponding source datasets. However, in both cases the external file with the results from the Bio-analytical lab for PK and from the Cardiac Safety Services group for ECG will contain all dates including those that are missing in the source datasets. The external files will be merged in with the source data files to create the corresponding SDTM domains, thereby allowing all dates to be populated.

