9.4.3 Safety Analyses

All safety analyses will be performed on the Safety Analysis Set.

Treatment-emergent adverse events (TEAEs) are defined as AEs that first occurred or worsened in severity after administration of study treatment.

Adverse events will be coded using the Medical Dictionary for Regulatory Activities (MedDRA). For each study treatment, numbers of TEAEs and incidence rates will be tabulated by preferred term and system organ class.

Treatment-emergent AEs by maximum severity, TEAEs by relationship to study treatment, SAEs, TEAEs leading to death, and TEAEs leading to discontinuation of study treatment will be tabulated for each study treatment.

All laboratory test results, vital signs measurements, and ECG results will be summarized for each treatment group using descriptive statistics at each visit for raw numbers and change from baseline.

Test results from otoscopy, tympanometry, nasal and epipharynx endoscopy, UPSIT olfactory test, and audiology pure tone hearing test will be listed and summarized as appropriate.

Additional details will be provided in SAP.

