17.1. ADVERSE EVENTS

An AE is defined as any untoward medical occurrence in a subject, temporally associated with the use of study treatment, whether or not considered related to the study treatment. An AE can therefore be any unfavorable and unintended sign (including an abnormal laboratory finding), symptom, or disease (new or exacerbated) temporally associated with the use of study treatment. All AEs will be coded to appropriate System Organ Class (SOC) and Preferred Term (PT) using Medical Dictionary for Regulatory Activities (MedDRA) central coding dictionary, Version 21.0.

Pre-treatment AEs are defined as AEs that begin before the initiation of the first dose of study drug administration on Day 1 but after obtaining informed consent and will be recorded as pre-treatment AEs. These events will be presented in the listings only and will not be included in the tabular summary of AEs.

Treatment-emergent adverse events (TEAEs) are defined as AEs that first occurred after the initiation of the first dose of study drug administration on Day 1 or a pre-treatment AE that worsened in severity. See APPENDIX 2 for handling of partial dates for AEs. In the rare case where it is not possible to assess treatment emergence, the AE will be classified as treatment emergent (i.e., the worst case).

Severity

AE severity will be classified as Mild, Moderate, or Severe as per protocol Appendix 4. TEAEs with missing severity will be classified as Severe. If subject reports a TEAE more than once within the same SOC/ PT, the AE with the worst-case severity will be used in the corresponding severity summaries.

Relationship to Study Medication

Relationship to study medication will be completed by the Investigator as per Protocol Appendix 4, classified as “Related” or “Not Related”. A TEAE is assessed as “Related” if there is reasonable/plausible possibility that the TEAE may have been caused by the study medication. A TEAE is assessed as “Not Related” if no causal relationship exists between the study medication and the TEAE, but an obvious alternative cause exists, e.g. the subject’s underlying medical condition or concomitant therapy. TEAEs with missing relationship to study medication will be regarded as “Related” to study medication. If a subject reports the same TEAE more than once within the same SOC/ PT, the AE with the worst-case relationship, i.e., “Related” to study medication, will be used in the corresponding relationship summaries.

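### The treatment-emergence table in SAP Appendix 2 omits the worsening part of the TEAE definition, so a pre-treatment AE that worsens on treatment can be classified two ways

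*SAP*

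**What the plan says.** SAP Section 17.1 defines a TEAE in two parts: an AE that first occurs after the first dose, "or a pre-treatment AE that worsened in severity". Protocol Section 9.4.3 and the protocol synopsis agree, defining TEAEs as "AEs that first occurred or worsened in severity after administration of study treatment".

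Section 17.1 also says of pre-treatment AEs: "These events will be presented in the listings only and will not be included in the tabular summary of AEs". It sends the reader to the appendix with "See APPENDIX 2 for handling of partial dates for AEs" and adds a default: "In the rare case where it is not possible to assess treatment emergence, the AE will be classified as treatment emergent".

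Appendix 2 is headed "PARTIAL AND MISSING DATE CONVENTIONS". Its AE table crosses four states of the start date with three states of the stop date (known, partial, missing). For a known start the rule is "If start date < study med start date, then not TEAE", whatever the stop date. For a start described as "Partial, but known components show that it cannot be on or after study med start date", the action is not TEAE for every stop date. No row mentions severity.

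**The concern.** The table is presented as the algorithm for treatment emergence, yet it implements only the first-occurrence part of the definition. Take an AE that is mild from Day -1, becomes moderate on Day 4 and resolves on Day 8. Section 17.1 makes it a TEAE. The table makes it not a TEAE if the start date is known, and a TEAE if the start date is missing.

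AEs are the first-listed primary endpoint (SAP Section 3.1), and every AE incidence table planned in Section 17.1 counts TEAEs. An event the table excludes would appear only in listings. Two programmers, each following the SAP, could therefore produce different tables for the primary endpoint.

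**Working it through.** **Branch count.** Four start-date states × three stop-date states = 12 branches. Apply each to an AE that starts before first dose, is still present on treatment and worsens there:

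| Start date | Stop known | Stop partial | Stop missing |
|---|---|---|---|
| Known, before first dose | not TEAE | not TEAE | not TEAE |
| Partial, must be before first dose | not TEAE | not TEAE | not TEAE |
| Partial, could be on or after first dose | TEAE | TEAE | TEAE |
| Missing | TEAE | TEAE | TEAE |

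- Rows 1 and 2 give 3 + 3 = 6 branches that exclude the event.
- Rows 3 and 4 give the other 12 − 6 = 6. A known stop date must fall on or after first dose, because the event is still present on treatment. A partial stop date is imputed to its latest possible date, which also falls there. A missing stop date is assumed TEAE. These rows include the event because of the stop-date test, not because they test for worsening.

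Dated examples give the same split: onset 1 to 28 days before first dose, worsening on Day 1, 4, 14 or 21, and resolution 0, 5 or 30 days later.

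**Does the default rescue rows 1 and 2?** No. It applies only when emergence cannot be assessed. In those rows the start is certainly before first dose, so the table gives a definite answer.

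**Does record-keeping rescue them?** It depends on a convention that is not stated. If the worsening is entered as a new record starting on the worsening date, that record can reach only 9 of the 12 branches (row 2 is impossible), and all 9 return TEAE. If a severity test is placed ahead of the date test, 0 of 12 branches exclude the event.

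**Size of one misclassification.** The step in reported incidence is 1/N, using the planned group sizes in SAP Table 1 and the pooled columns in SAP Appendix 1:

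- OP0201 30 mg or 60 mg: 1/12 = 8.3 points
- All Active: 1/24 = 4.2 points
- All Placebo: 1/6 = 16.7 points
- All Subjects, where shown: 1/30 = 3.3 points

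Each figure applies only if the subject has no other TEAE in the same table row.

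**The case against.** The best defence is that Section 17.1 already states the rule and uses Appendix 2 only for partial dates, as the appendix heading suggests. On that reading the table places a record in time and does not override the definition.

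Several passages also suggest that a worsening would get its own record:

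- Protocol Appendix 4 counts new or exacerbated disease as an AE, asks for each event to be recorded separately, and assigns each AE one intensity category.
- The same appendix excludes day-to-day fluctuation of conditions found at study start only when they do not worsen.
- SAP Section 17.1 expects the same term to be reported more than once and takes the worst severity.

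The instruction in Protocol Appendix 4 to put updates in the original CRF is thin evidence against this, since it does not mention severity. If severity is simply overwritten, the change may not be identifiable, and then Section 17.1 could not be programmed either.

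The impact may also be remote. Subjects are screened healthy volunteers, safety comparisons between groups are not planned unless otherwise specified (SAP Section 17), and the event stays in listings. The 1/N steps would apply to any misclassified event, and 6 of 12 is one rule repeated across date states, not a probability.

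The points about impact stand. The defence of the text does not settle the matter. The known-start rows rule on complete dates without condition, and even on the narrow reading row 2 is a true partial-date case that excludes a worsened event. No passage says that a worsening of a recorded pre-treatment AE becomes a new record with an on-treatment start. Section 17.1 itself speaks of a pre-treatment AE that worsened, which treats it as the same event.

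**Conclusion.** The concern holds. The Appendix 2 table contradicts the TEAE definition in SAP Section 17.1 and Protocol Section 9.4.3 for pre-treatment AEs that worsen on treatment, and nothing states which prevails. Confidence is high for the gap in the text and the branch count, not for any effect on results.

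An effect requires the full chain: a pre-treatment AE occurs, continues into dosing, worsens, stays on its original record and is classified from the table. The documents provide for recording and listing pre-treatment AEs (Protocol Section 8.3.1, SAP Section 6.1) but do not show that any will occur. The size per affected subject assumes that the planned group sizes are met. This should be corrected, because it concerns the first-listed primary endpoint and the correction is small.

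**What to change.** Use one of two remedies.

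1. Add a severity rule to Appendix 2, ahead of the date test: an AE that starts before first dose and increases in severity on or after first dose is a TEAE with onset at the date of worsening; if worsening is documented but undated, it is a TEAE; a pre-treatment AE with no documented worsening stays non-TEAE.
2. Limit the table to first occurrence, state that Section 17.1 governs worsening, and state that worsening of a pre-treatment AE is entered as a new AE record dated at the worsening.

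The cost is a sentence or two in Appendix 2 and a matching line in the AE dataset specification, before unblinding. The first remedy needs severity change to be identifiable in the AE data. The eCRF is not among the documents; if it does not capture severity change, the second remedy is the workable one.

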- q Study subjects need to be trained on study treatment administration on Day -1 or on Day 1, prior to the first dose.
- r Study treatment dosing recommendation: the first dose at 9:00 am, second dose at 16:00 pm and the third dose at 23:00 pm.

- s PK sample timing Cohort B only: Day 1: 30 and 60 minutes prior to the first dose, Day 14: 30 minutes prior to the last dose and 5, 20, 35, 50 minutes following the last dose on Day 14. The 5-minute PK sample should be collected within ± 2 minutes of the scheduled time and the 20-minute PK sample should be collected within $+5$ minutes of the scheduled time. All other PK samples should be collected within ± 5 minutes of the scheduled time.
- t To be completed before discharge from the study center on the morning of Day 15 (See Protocol Appendix 7 for an example).
- u This assessment is needed only if subjects discontinue the study prior to completing the questionnaire on Day 15.

Document: Statistical Analysis Plan
Author: [REDACTED]

Version Number: 2.0
Version Date: 03APR2019

[REDACTED]
[REDACTED]

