14. MEDICATIONS

All medication usage will be coded using the World Health Organization Drug Dictionary (WHO-DD) version 01MAR2018E Format B-2 and listed.

- Prior medications are medications which stopped prior to the first dose of study medication.
- Concomitant medications are medications which were taken during the treatment period, or specifically:
 - started on or after the date and time of first dose of study medication or
 - started prior to the first dose of study medication and were continued after the first dose of study medication

See APPENDIX 2 for handling of partial dates for medications, in the case where it is not possible to define a medication as prior or concomitant, the medication will be classified by the worst case; i.e., concomitant.

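### SAP Appendix 2 classifies adverse events by calendar date alone, contradicting the first-dose definition in SAP 17.1 for Day 1 pre-dose onsets and for pre-treatment events that worsen

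*SAP*

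**What the plan says.** SAP 17.1 sets the boundary at a moment. It states: "Pre-treatment AEs are defined as AEs that begin before the initiation of the first dose of study drug administration on Day 1", provided consent has been obtained, and sends these events to listings and not to the summary tables. TEAEs are "AEs that first occurred after the initiation of the first dose of study drug administration on Day 1", together with pre-treatment events whose severity increased. Protocol 9.4.3 likewise ties treatment emergence to onset or worsening after administration. For detail, 17.1 says: "See APPENDIX 2 for handling of partial dates for AEs". It adds a worst-case default: an event whose treatment emergence cannot be assessed counts as a TEAE.

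SAP Appendix 2 is headed "PARTIAL AND MISSING DATE CONVENTIONS", but its AE table also covers fully known start dates, with known, partial or missing stop dates. In all three of those rows a start date earlier than the study medication start date gives not TEAE, and otherwise: "If start date >= study med start date, then TEAE". Clock time appears nowhere in the AE table, and no row deals with worsening.

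Protocol 6.1 plans the first daily dose for 09:00. In SAP 4.2, Table 2, footnote s gives: "PK sample timing Cohort B only: Day 1: 30 and 60 minutes prior to the first dose". Footnote i gives Cohort B triplicate ECGs at the same two Day 1 times, and Cohort A one single ECG before the first dose. SAP 7.2 pools placebo subjects from both cohorts.

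**The concern.** Adverse events are the first-listed primary endpoint in SAP 3.1, and the TEAE flag decides which of them reach the tables. The SAP has two rules for that flag, and they disagree on events that need no imputation. Appendix 2 is the only step-by-step algorithm, so a programmer could reasonably apply it to every event.

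The disagreement runs in both directions. A Day 1 event that began before any drug was given can enter the TEAE tables, and an event that worsened on treatment can be left out. The first kind of error may also be uneven across dose groups, because the Day 1 pre-dose blood draws are confined to Cohort B.

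**Working it through.** The documents state no figure on this point, so there is nothing to reproduce. The check applies both rules to the same events and then counts who is exposed.

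**Step 1: the two rules side by side, first dose at 09:00 on Day 1**

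| Event | SAP 17.1 | Appendix 2 as written |
|---|---|---|
| Onset Day -1, 20:00, no worsening | pre-treatment | not TEAE |
| Onset Day -1, worsens after first dose | TEAE | not TEAE |
| Onset Day 1, 08:00 | pre-treatment | TEAE |
| Onset Day 1, 08:30 | pre-treatment | TEAE |
| Onset Day 1, 09:05 | TEAE | TEAE |

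The rules conflict for known onsets between 00:00 and 09:00 on Day 1, a 9-hour window, and for every pre-treatment event that later worsens and keeps its earlier start date.

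**Step 2: Day 1 procedures before the first dose (SAP 4.2, footnotes i and s)**

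- Cohort B: 2 PK draws, and 2 × 3 = 6 ECG tracings.
- Cohort A: 0 PK draws and 1 ECG tracing.

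The pre-dose ENT examinations are on Day -1 in both cohorts, so a date-only rule does not reclassify events starting then.

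**Step 3: share of each analysis group with pre-dose draws**

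Each cohort of 15 splits 4:1 into 12 OP0201 and 3 placebo (SAP 4.1, Table 1). Let q be the unknown probability that a Cohort B subject has an adverse event from the draws before the first dose. The expected share of subjects with a misclassified event is then:

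- OP0201 60 mg: 12q/12 = q
- OP0201 30 mg: 0/12 = 0
- Pooled placebo: 3q/6 = q/2
- All active: 12q/24 = q/2

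The 60 mg group therefore exceeds 30 mg by q and pooled placebo by q/2. All active minus all placebo is q/2 − q/2 = 0.

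**Step 4: weight of one subject**

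One affected subject is 1/12 = 8.3 percentage points of a dose group and 1/6 = 16.7 points of pooled placebo.

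**Step 5: effect of comparing date and time**

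The 08:00 and 08:30 onsets become pre-treatment, the 09:05 onset stays a TEAE, and the excess in Step 3 falls to 0 in every group for events with a known onset time. A pre-dose event on Day 1 that worsens after dosing would then also depend on a worsening row to remain a TEAE, so the two edits belong together.

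**The case against.** The strongest reply is that Appendix 2 is a fallback. Its title and the cross-reference in 17.1 limit it to incomplete dates, so a programmer following 17.1 would class an 08:30 onset as pre-treatment. This stands in part: a reader might infer that Day 1 pre-dose events are definitely counted as TEAEs, and the documents do not establish that. They establish two conflicting instructions, because the table has its own rows for fully known dates.

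A second tempting inference is a false dose response. The documents do not support it. They give no rate of pre-dose procedure events, so any probability merely restates an assumption: taking 2% to 10% per subject, 1 − (1 − q)^12 gives 21.5% to 71.8% for at least one affected subject on 60 mg. Moreover, Cohort B has 7 PK draws, of which only 2 precede the first dose. Events from the 5 on Day 14 are TEAEs under either rule, and Cohort A has no such draws, so most of the imbalance is a design feature. Related TEAEs are tabulated separately, and individual events are listed.

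A third inference is that AEs were treated less carefully than medications, since SAP 14 refers to those "started on or after the date and time of first dose of study medication". The contrast is weak: the medication table in Appendix 2 is also date-only.

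Finally, the documents do not say whether AE onset time is collected. Where it is missing, counting a Day 1 event as a TEAE follows the worst-case default in 17.1. That default does not cover an event whose time is known.

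**Conclusion.** The contradiction is real and rests on the text alone. Programmed as written, Appendix 2 would tabulate a known pre-dose Day 1 onset as a TEAE and would drop a pre-treatment event that worsened, both against 17.1. It is therefore not uniformly conservative.

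The numerical size is unknown. Misclassification arising from the pre-dose draws could reach 12/12 subjects on 60 mg, 0/12 on 30 mg and 3/6 on pooled placebo, at 8.3 points per affected subject in a 12-subject group. It would be uneven in 60 mg versus 30 mg and in 60 mg versus pooled placebo, and balanced in expectation in all active versus all placebo.

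This rests on three assumptions: the Appendix 2 table is applied to known dates; the first dose is given near 09:00, which footnote r of the schedule calls a recommendation; and, for the uneven part, the draws cause some events before dosing. The worsening error also assumes that a worsened event keeps its original start date, which the documents do not settle. The point is a clarification worth making because it concerns a primary endpoint; it is not evidence that the safety comparison is biased.

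**What to change.** State in the SAP that the 17.1 definitions govern, and amend the Appendix 2 AE table as follows:

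- When the start date equals the first-dose date and the onset time is known, compare onset date and time with those of the first dose: before is pre-treatment, at or after is TEAE.
- When the start date equals the first-dose date and the onset time is missing, keep the TEAE default.
- Add a row making a pre-treatment AE that worsens in severity after the first dose a TEAE.

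The cost is a few lines of SAP text and the matching code. No eCRF change is needed, since events without a recorded time already fall under the worst-case default. The limitation is that the time comparison does nothing for Day 1 events that lack an onset time.
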